Evaluation of antiviral indications and therapeutic effect by liver biopsy combined with clinical trial parameters on chronic HBV infection with different transaminase levels

Study Protocol with Statistical Analysis Plan (SAP) and Informed Consent Form (ICF)

October 25, 2018

Evaluation of antiviral indications and therapeutic effect by liver biopsy combined with clinical trial parameters on chronic HBV infection with different transaminase levels

Study Protocol
(Pages 2-5)

October 25, 2018

Study Protocol

Study titled 'Evaluation of antiviral indications and therapeutic effect by liver biopsy combined with clinical trial parameters on chronic HBV infection with different transaminase levels' was approved by the First Affiliated Hospital of Xi'an Jiaotong University of Medicine Clinical Researches Ethics Committee meeting on 10/19/2018 with approval number: XJTU1AF2018LSK-146.

The patients or legal representatives of the children who participated in the study were informed about the aim and the programs to be applied throughout the study. Volunteer Information Form has been signed and approved in accordance with the standards deemed appropriate by the First Affiliated Hospital of Xi'an Jiaotong University of Medicine Clinical Researches Ethics Committee (This form can be seen on Informed Consent Form (ICF) section). The study was conducted in accordance with the Declaration of Helsinki.

Hypothesis of the Study

H0: Initiating treatment is not recommend for the patients with ALT <2ULN, high viral load, because some studies considered that the potential harms of long-term therapy, including cost, low response rates, drug adverse effects and development of resistance, outweigh its benefits.

H1: Initiating treatment is recommend for the patients with ALT <2ULN, high viral load, because some studies considered that high levels of serum HBV DNA (>10⁴copies/ml) are associated with a high risk of hepatocellular carcinoma (HCC) and the histological activity and HBV-specific immune responses do also occur in this

phase.

Inclusion Criteria

(1)Patients with a history of chronic HBV infections,defined as those in whom presence of serum hepatitis B surface(HBsAg) for more than 6 months.

(2)All patients had underwent a liver biopsy.

(3)All patients signed the informed consent.

(4)No history of interferon or Nucleoside analogue treatment.

Exclusion Criteria

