(1)Co-infection with human immunodeficiency virus(HIV),hepatitis A virus(HAV),hepatitis C virus(HCV),hepatitis D virus(HDV) and/or hepatitis E virus(HEV).

(2)Decompensated cirrhosis.

(3)History of liver transplantation.

(4)History of hepatocellular carcinoma(HCC).

(5)Having received antiviral treatment.

(6)Taking immunoregulation drugs such as cytotoxic agents and hormones.

(7)Use of hepatotoxic drugs or regular consumption of alcohol.

(8)Autoimmune disease or antinuclear antibody titers higher than 1:160.

(9)And other chronic liver disease.

[figure not shown]
(10)Incomplete data.

Applied Evaluations

[figure not shown]
Response indexes as the follows: virological response(HBV DNA below the

detection limit);HBsAg response(HBsAg decline \geq 0.5log₁₀ IU/ml);HBeAg seroconversion(HBeAg loss and HBeAb appearance);biochemical response(ALT normalization);LSM response(LSM decrease as at least a 1-kPa).

Research programme

Research group

Evaluation of antiviral indications and therapeutic effect by liver biopsy combined with clinical trial parameters on chronic HBV infection with different transaminase levels

Statistical Analysis Plan (SAP)

(Pages 6-7)

October 25, 2018

Statistical Analysis Plan (SAP)

The statistical program Statistical Package for Social Sciences (SPSS) Version 20.0 (SPSS Inc., Chicago, IL, USA) was used in the data analysis of the study. The p value of $p < 0.05$ was considered to be statistically significant in the data analysis. Continuous quantitative variables were expressed as mean \pm standard deviation (SD) for normal distributions or median and interquartile range (IQR) (25th-75th percentile) for abnormal distributions, which were assessed with an independent samples T test or the Mann-Whitney U test as comparison of two sets of samples while comparison of multiple samples were assessed with ANOVAs or Kruskal-Wallis tests. Repeated measures data of general linear model were used to calculate variation trend between treated and untreated follow-up patients. Categorical variables were expressed as percentages that were analyzed using the χ^2 test, such as gender, HBV genotype, ALT, HBsAg, HBeAg, HBeAb, HBcAb and LSM.

The receiver operating characteristic (ROC) curve was plotted in order to find the most appropriate HBV DNA, HBsAg, HBeAg cutoff value for diagnosis of patients with ALT < 2 ULN who are chronic HBV infection or chronic hepatitis B.

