Univariate logistic regression and multivariate forward stepwise logistic regression were used to assess the incidences of antiviral responses, such as HBV DNA response, serological responses, biochemical response

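### The SAP seeks ROC cutoffs for HBV DNA, HBsAg and HBeAg but states no HBeAg subgroup, cutoff rule or internal validation

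*Combined protocol and SAP*

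**What the plan says.** The ROC paragraph of the SAP is one complete sentence. It opens "The receiver operating characteristic (ROC) curve was plotted in order to" and gives the purpose: to "find the most appropriate HBV DNA, HBsAg, HBeAg cutoff value for diagnosis of patients with ALT < 2 ULN". The two classes to be told apart are given by "who are chronic HBV infection or chronic hepatitis B". The sentence names no HBeAg subgroup, no criterion for the best cutoff and no internal validation.

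Other places bear on the HBeAg mix:

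- Inclusion Criterion (1) asks for chronic HBV infection, "defined as those in whom presence of serum hepatitis B surface(HBsAg) for more than 6 months". Neither the inclusion nor the exclusion list restricts HBeAg status.
- The SAP lists HBeAg among the categorical variables ("such as gender, HBV genotype, ALT, HBsAg, HBeAg, HBeAb, HBcAb and LSM"), and Applied Evaluations includes "HBeAg seroconversion(HBeAg loss and HBeAb appearance" as a response. The second presupposes some HBeAg-positive patients.
- H1 reads "Initiating treatment is recommend for the patients with ALT <2ULN, high viral load". The ROC sentence carries the ALT limit but not the viral-load condition, which could change the HBeAg mix.

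After the ROC paragraph the SAP turns to response models ("Univariate logistic regression and multivariate forward stepwise logistic regression were used to assess the incidences of antiviral responses") and breaks off. Figures are missing around Applied Evaluations, and Research programme and Research group are headings without text. HBeAg strata or validation may have been described there.

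**The concern.** Two separate problems arise if the ROC sentence is followed as it reads.

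**Pooling.** When a marker's level depends on HBeAg status, the best cutoff in HBeAg-positive patients differs from the best in HBeAg-negative patients. A single cutoff is then a compromise that may suit neither group. The pooled AUC does not reveal this, because between-group differences can raise it. For HBeAg itself, a cutoff value implies a quantitative level, and HBeAg-negative patients lie below the positivity threshold by definition. A pooled HBeAg curve therefore partly re-expresses HBeAg status.

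**Optimism.** A cutoff picked because it performs best in a sample, and then judged in that sample, looks better on average than it will in new patients.

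The cutoffs are meant to separate chronic HBV infection from chronic hepatitis B when ALT is below 2 ULN. That is the antiviral-indication question in the title, so overstated or misplaced cutoffs affect the study's main message.

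**Working it through.** The documents give no sample size, AUC, cutoff, prevalence, HBeAg mix or marker distribution. There is no planned figure to reproduce, and **every input below is an assumption**.

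**1. Pooling (analytic)**

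The marker is normal with SD 1 in each group, and the within-stratum AUC is 0.76. The case-control separation is d = √2 × z(0.76) = 1.414 × 0.706 = 0.999. Lower-marker stratum: controls at 0, cases at d. Higher-marker stratum: both raised by s. The cutoff c maximises the pooled Youden index, J = sensitivity + specificity − 1.

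- Higher stratum: sensitivity Φ(s + d − c), specificity Φ(c − s).
- Lower stratum: sensitivity Φ(d − c), specificity Φ(c).

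With a 50% mix and equal prevalence (0.4), symmetry gives c = (s + d)/2 for the shifts shown. For s = 1, c = 0.9995. The higher stratum has Φ(0.9995) = 0.841 and Φ(−0.0005) = 0.500, and the lower stratum has the reverse.

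| Shift s | Pooled AUC | Higher: sens/spec | Lower: sens/spec | J in each stratum |
|---|---|---|---|---|
| 0 | 0.760 | 0.691/0.691 | 0.691/0.691 | 0.38 |
| 0.25 | 0.758 | 0.734/0.646 | 0.646/0.734 | 0.38 |
| 0.5 | 0.753 | 0.773/0.598 | 0.598/0.773 | 0.37 |
| 1 | 0.735 | 0.841/0.500 | 0.500/0.841 | 0.34 |
| 2 | 0.686 | 0.933/0.308 | 0.308/0.933 | 0.24 |

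With no shift there is no distortion. An unequal mix moves the loss to the smaller stratum. With 30% in the higher stratum and s = 1, the higher stratum has 0.893/0.403 (J 0.296) and the lower 0.597/0.775 (J 0.372).

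The pooled AUC can rise while the cutoff is misplaced. Take s = 1, a 50% mix, and prevalence 0.6 in the higher and 0.3 in the lower stratum. Cases then split 2/3 higher and 1/3 lower; controls split 4/11 and 7/11. The pooled AUC is

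(8 × 0.760 + 14 × 0.921 + 4 × 0.500 + 7 × 0.760)/33 = 0.797,

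where 0.921 = Φ(1.999/√2) compares higher cases with lower controls, and 0.500 compares lower cases with higher controls. This exceeds 0.76, but the pooled cutoff gives 0.838/0.506 in the higher stratum and 0.494/0.845 in the lower.

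At s = 2 with prevalence reversed (0.3 higher, 0.6 lower), the cutoff can miss both stratum optima (2.50 and 0.50) on the same side: 0.17 at a 50% mix and 2.72 at 70% in the higher stratum. The pooled AUCs there are only 0.566 and 0.591, so the poor performance would be visible.

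**2. Optimism (simulation)**

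Binormal marker, prevalence 0.4, cutoff chosen by maximum J in the sample, 4,000 data sets per cell. Entries are mean apparent J, mean true J at that cutoff, and the difference.

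| n | True AUC 0.65 | True AUC 0.75 |
|---|---|---|
| 50 | 0.335 − 0.188 = 0.147 | 0.468 − 0.335 = 0.133 |
| 100 | 0.297 − 0.195 = 0.102 | 0.434 − 0.345 = 0.089 |
| 200 | 0.271 − 0.200 = 0.071 | 0.412 − 0.352 = 0.060 |
| 400 | 0.252 − 0.205 = 0.047 | 0.396 − 0.357 = 0.039 |
| 800 | 0.239 − 0.208 = 0.031 | 0.386 − 0.361 = 0.025 |

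At AUC 0.75 and n=100, sensitivity appears as 0.719 against a true 0.660, and specificity as 0.715 against 0.685. The apparent J exceeded the true one in 79% to 93% of data sets, so not always. A second grid (case share 0.3 or 0.5, true AUC 0.6 to 0.8, n from 50 to 800) gave positive mean optimism in all 30 cells, from 0.17 down to 0.02.

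**3. Does a bootstrap correction work?**

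400 data sets with 200 resamples each, reselecting the cutoff in every resample. The share of optimism removed is (apparent − corrected)/(apparent − true).

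- AUC 0.65, n=50: (0.331 − 0.236)/(0.331 − 0.184) = 65%.
- AUC 0.65, n=200: (0.266 − 0.217)/(0.266 − 0.200) = 74%.
- AUC 0.75, n=50: (0.467 − 0.380)/(0.467 − 0.333) = 65%.
- AUC 0.75, n=200: (0.411 − 0.368)/(0.411 − 0.353) = 74%.

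**The case against.** The strongest reply is that the gap cannot be proved. The places where patient groups would be defined are empty, figures are lost, and the SAP stops mid-sentence. One general ROC sentence does not show that the curve was pooled. This stands, so the point is confined to the readable SAP.

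Second, pooling is a trade-off as well as a loss. In the tables, lower sensitivity in one stratum comes with higher specificity. From the unshifted J of 0.383, the loss is about 0.003 at 0.25 SD, 0.011 at 0.5 SD and 0.04 at 1 SD. Splitting n=100 into strata of 50 raises optimism by 0.04 to 0.05 and lowers true J by 0.007 to 0.010. Stratum-specific cutoffs would therefore gain little or nothing at small shifts. This also stands. It is a reason to show stratum results beside the pooled one, not to replace it. It does not remove the case for looking, since nobody can tell from the pooled AUC which situation applies.

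Third, the optimism figures assume a rule such as Youden and that sensitivity and specificity are reported. The SAP states neither, and a rule fixing one of them in advance could give less optimism. That is true, and it supports naming the rule. A diagnostic cutoff is of little use without its sensitivity and specificity.

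Fourth, a single-marker AUC is free of this optimism only if the marker's direction is fixed beforehand. With direction chosen from the data at n=50 and 40% cases, the mean AUC was 0.57 for a true 0.50 and 0.58 for a true 0.55. The effect was negligible from 0.65 upward. This qualification is accepted.

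**Conclusion.** The concern holds for the readable SAP. A complete ROC sentence seeks cutoffs for three markers in a population that may be HBeAg-mixed, without a subgroup, a selection rule or validation.

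The optimism point is the firmer one. Given a cutoff that maximises accuracy in the sample, it applies on average at any sample size, is material at 50 to 200 patients and is small by 800. The pooling point is conditional: nothing is lost without a marker shift, little at up to 0.5 SD, and considerably more at 1 to 2 SD or with an unequal mix. None of the figures estimates what happened in this study. The change is a worthwhile, inexpensive improvement, not the correction of an error.

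**What to change.** Add to the ROC paragraph of the SAP:

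- Report the HBV DNA and HBsAg ROC analyses by HBeAg status alongside any pooled result, and the quantitative HBeAg ROC in HBeAg-positive patients.
- State in advance one cutoff criterion (Youden is one option) and the direction of each marker.
- Report bootstrap optimism-corrected sensitivity and specificity at the selected cutoff, repeating the selection in each resample, with 95% confidence intervals for the AUC and the cutoff. With direction fixed, the single-marker AUC needs no optimism correction.
- State whether the viral-load condition in the hypotheses applies to this analysis.
- If a lost part of the document already gives HBeAg strata or validation, refer to it here.

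The cost is a few sentences and a short bootstrap script; no new data are needed. Stratum results will have wider intervals and more optimism before correction, reported accuracy will be slightly lower, and the bootstrap removes about two thirds to three quarters of the optimism, not all of it.

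### In the text shown, forward stepwise selection is the only multivariable method for the binary antiviral responses; a short prespecified forced-entry model should be the main one

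*Combined protocol and SAP*

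**What the plan says.** The last sentence of the SAP that can be read gives the method: "Univariate logistic regression and multivariate forward stepwise logistic regression were used to assess the incidences of antiviral responses". It continues "such as HBV DNA response, serological responses, biochemical response" and then stops without a full stop. No candidate list, entry or removal threshold, or forced term appears in what can be read. Nothing is shown under Research programme or Research group.

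Under Applied Evaluations the protocol defines five yes/no responses. The first two concern HBV DNA and HBsAg; the other three are "HBeAg seroconversion(HBeAg loss and HBeAb appearance);biochemical response(ALT normalization);LSM response(LSM decrease as at least a 1-kPa".

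Three places suggest which terms might matter, although none says that they are in the logistic model:
- The title speaks of "therapeutic effect by liver biopsy combined with clinical trial parameters on chronic HBV infection with different transaminase levels".
- H1 reads "Initiating treatment is recommend for the patients with ALT <2ULN, high viral load".
- The SAP says "Repeated measures data of general linear model were used to calculate variation trend between treated and untreated follow-up patients".

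The SAP also lists variables for the chi-square test, "such as gender, HBV genotype, ALT, HBsAg, HBeAg, HBeAb, HBcAb and LSM", but does not call them candidates for the regression.

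**The concern.** Forward selection lets a p-value from the same data decide which variables appear in the adjusted model. Three things can follow.

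1. The variable that the reader cares about may be absent, so no adjusted odds ratio is reported for it. A real confounder may also be absent, so that an odds ratio that is reported is not adjusted for it.
2. Variables unrelated to response can enter and be read as predictors.
3. A term is shown only when it is significant, so its odds ratio tends to be too far from 1, and the usual CI takes no account of the selection.

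No randomisation is described in the text shown, so any comparison of treated with untreated patients or of ALT groups depends on adjustment. If the model is only a search for predictors of response, the second and third consequences still apply.

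**Working it through.** **Is there another adjusted model?** The other methods in the SAP are the t test, Mann-Whitney test, ANOVA, Kruskal-Wallis test, chi-square test, ROC curves and a repeated-measures general linear model for trends. None is a covariate-adjusted model of a binary response. Univariate logistic regression adjusts for nothing. Stepwise selection is therefore the only visible route to an adjusted odds ratio.

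**Inputs.** The documents give the 0.05 significance level and SPSS 20.0. They show no sample size, event rate, effect size or selection threshold, so there is no figure of the plan to reproduce. Everything below is assumed unless stated otherwise.

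**Noise predictors.** With k independent null candidates tested at 0.05, P(at least one enters) = 1 - 0.95^k.
- k = 7: 1 - 0.95^7 = 30.2%.
- k = 8 (the number of variables in the chi-square list): 1 - 0.95^8 = 33.7%.

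**Simulation.** 1000 data sets per setting; binary exposure (50%); one confounder with latent correlation 0.4 to the exposure and OR 1.3 or 1.6 per SD; seven null candidates; 40% response; score-test entry at 0.05 and Wald removal at 0.10. Each cell gives the result for confounder OR 1.3 / 1.6.

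| True exposure OR | n | Exposure missing | Confounder missing |
|---|---|---|---|
| 1.5 | 150 | 69.9% / 75.8% | 61.2% / 19.7% |
| 1.5 | 300 | 58.7% / 64.1% | 37.7% / 3.4% |
| 1.5 | 600 | 35.2% / 36.4% | 15.8% / 0% |
| 2.0 | 150 | 41.2% / 46.0% | 62.0% / 25.3% |
| 2.0 | 300 | 20.1% / 22.6% | 45.3% / 5.8% |
| 2.0 | 600 | 2.4% / 2.8% | 16.7% / 0.1% |
| 3.0 | 150 | 9.6% / 13.5% | 68.7% / 29.2% |
| 3.0 | 300 | 0.5% / 1.2% | 48.5% / 7.9% |
| 3.0 | 600 | 0% / 0.1% | 19.0% / 0% |

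At least one null candidate entered in 29-35% of runs (26-30% with the null candidates correlated 0.3), in line with the formula. At n=300 and true OR 2.0, the exposure was kept without the confounder in 43.3% / 5.8% of runs, with a mean reported OR of 2.48 / 2.71.

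**Reported odds ratios** (exponent of the mean log-OR, with 95% CI coverage). Forced entry here means the exposure, the confounder and three null terms, averaged over all runs.

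| Setting | Stepwise, when the exposure is shown | Forced entry, all runs |
|---|---|---|
| n=150, true 1.5 | 2.56 / 2.66 (82.4% / 76.4%) | 1.55 / 1.54 (94.7% / 95.2%) |
| n=150, true 2.0 | 2.92 / 2.90 (89.3% / 89.6%) | 2.10 / 2.07 (94.7% / 94.8%) |
| n=600, true 2.0 | 2.07 / 2.04 (94.3% / 96.9%) | coverage 94.1-95.8% over all settings with OR 1.5 or more |

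**Like for like.** That table sets filtered results beside unfiltered ones. If forced entry is also restricted to its significant runs (1,500 runs, confounder OR 1.3), the gap nearly closes:
- n=150, true 1.5: stepwise 2.57, forced 2.54 (coverage 0.81 and 0.86).
- n=150, true 2.0: 2.86 and 2.82.
- n=300, true 2.0: 2.30 and 2.21.

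**Wrong covariates.** Forcing five terms that omit the true confounder, at n=150 and true OR 1.5, gives 1.80 (confounder OR 1.3) or 2.00 (confounder OR 1.6), with coverage 0.92 or 0.87.

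**Error rate and power.** With a null exposure, stepwise admits it in 5.2-7.1% of runs, and forced entry finds it significant in 5.2-6.6%. At n=300 and true OR 2.0, forced entry is non-significant in 23.8% / 22.5% of runs, against 20.1% / 22.6% missing from stepwise.

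**Second set of assumptions.** With n = 100 / 200 / 400, treatment OR 2, confounder log-OR 0.4 per SD, latent correlation 0.3 and no removal step, stepwise keeps treatment in 37.6% / 62.7% / 89.3% of runs, with mean OR 3.47 / 2.58 / 2.12. Forced entry over all runs gives 2.04 / 2.04 / 2.02 and is significant in 35.5% / 63.2% / 90.6%. The pattern is the same.

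**The case against.** The strongest reply is that the model's terms and purpose cannot be seen. The one sentence about it is cut off, and candidate or forced terms may stand in the missing text. A reader might infer that the plan fails to specify its covariates, or that it lets treatment or ALT group fall out of the model. The documents support neither. They do not say that treatment or ALT group is a candidate, and text lost in extraction cannot be counted as absent from the plan. A search for predictors, perhaps in treated patients only, fits the wording equally well. The comparison of treated with untreated patients is assigned to the repeated-measures model, although that model concerns trends. This objection stands and limits the point to the choice of method, which is stated.

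A second reply is that the inflated odds ratios are not mainly the work of the stepwise algorithm. That is right: the like-for-like figures show that most of the inflation is significance filtering. The benefit of forced entry comes from reporting every estimate.

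A third is that forced entry does well in the simulation because it is given the true confounder. That also stands. Coverage of about 95% is a best case.

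These replies narrow the point but do not remove it. Under any purpose of the model, noise terms can enter, and terms are shown because they are significant.

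**Conclusion.** The point holds as a cheap improvement to the analysis method. In the text shown, stepwise selection is the only multivariable method for the binary responses, and a short prespecified forced-entry model with full reporting is better.

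How much it matters here cannot be calculated, because no sample size, event rate or effect is shown. Under the assumed inputs the effect is large at n=150. At n=600 it is small for a true OR of 2.0 or more (exposure missing in 0-3% of runs), although an exposure with OR 1.5 is still missing in 35-36% and a weak confounder in 16-19%. Entry of at least one noise term, at about 30%, depends on the number of null candidates (seven assumed) and hardly on sample size.

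A reader might go further and infer that stepwise selection inflates the false-positive rate for the exposure, or that forced entry would detect more. The figures support neither. The gain is an adjusted estimate and CI that do not depend on selection and are reported whether or not significant. That estimate is only as good as the chosen covariates, and it does not remove confounding by unmeasured reasons for treatment.

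**What to change.** For each response, make the main multivariable model a forced-entry logistic model (SPSS ENTER) with a short set of baseline covariates already collected, named in the SAP and chosen on subject-matter grounds rather than from the univariate results.

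- Include ALT group where the model spans ALT groups, and treatment where treated and untreated patients are both analysed.
- Include the baseline value of the outcome where relevant, for example baseline LSM for the LSM response. HBV DNA, HBsAg, HBeAg status and biopsy result are other examples.
- Limit the number of terms by the events, for example one per 10 in the rarer outcome class. With an assumed n=150, a 40% response gives 150 x 0.40 = 60 events and six terms; 20% gives 30 events and three terms.
- Report every odds ratio with its 95% CI whether or not significant.
- Label any stepwise model exploratory.

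If the unseen part of the SAP already sets out such a model, no change is needed.

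The cost is SAP wording: the data are the same, and ENTER is in the same SPSS procedure. The downside is that non-significant covariates stay in and CIs may be slightly wider.

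Three secondary points can be settled in the same edit but are not part of the main claim: fit the seroconversion and ALT-normalisation models only in patients who can have the event; use a penalised (Firth) fit if there is separation, which may need an add-on or another package; and describe the p-values across the several responses as exploratory unless a multiplicity adjustment is applied.
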